# 8.7. Written Informed Consent

Each subject is required to provide written informed consent prior to undergoing any study procedures. A copy of the signed and dated informed consent (in a language in which the subject is fluent) is required to be given to the subject. If a subject withdraws consent, data collected up to the time of discontinuation will be used to evaluate study results.

### 8.8. Assessments

The Schedule of Assessments is presented in Table 1.

Clinical laboratory evaluations will be performed by a central laboratory. All clinical and laboratory evaluations, procedures related to inclusion/exclusion criteria, or performed during treatment must be reviewed, initialed and dated by the Principal Investigator or appropriate designee listed on Form FDA 1572.

### 8.8.1. Study Assessments by Visit

The following is a summary of assessments by study visit.

### 8.8.1.1. Screening Phase (up to -120 to -7 days)

### Visit 1: Screening

During the Screening Phase, once the informed consent form is signed, the following assessments will be performed/collected:

- Inclusion/Exclusion review
- Medical history
- Body height/weight
- Waist circumference
- Vital signs
- Physical examination
- Electrocardiogram (12-lead)
- Fasting safety labs chemistry (including CPK, liver enzymes, lipid panel) hematology, coagulation profile, and urinalysis labs
- CK-18 biomarker
- Liver MRI (can be scheduled on separate date)
- Serum  $\beta$ -hCG (pre-menopausal females)
- Fib-4 Index
- NAFLD fibrosis score
- Prior/concomitant medication review
- Alcohol consumption questionnaire

### Visit 2: Laboratory visit (-1 week ± 5 days)

Fasting safety labs and serum  $\beta$ -hCG (for pre-menopausal females) will be repeated around 1 week prior to Day 1 Baseline visit.

# 8.8.1.2. Treatment Phase (12 weeks)

Subjects who complete all of the screening assessments will return to the clinic on Treatment Day1 (Baseline) to repeat laboratory tests and physical assessments. Subjects who continue to be eligible will be enrolled to receive MN-001 250 mg qd for 4 weeks and then increase their dosage to 250 mg bid (500 mg/d) for the remaining 8 weeks (total dosing of 12 weeks). Subjects will receive their first dose of study medication on Day 1 at the clinic.

Subjects will enter the clinic in the morning prior to breakfast. Once the pre-dose fasting labs have been completed, subjects will be given breakfast.

### Visit 3: Baseline Day 1

- Inclusion/Exclusion review
- Body weight/waist circumference
- Vital signs
- Physical Examination
- 12-lead ECG at hour 1.5 (± 30 minutes) post dose
- Blood sample for Cholesterol efflux capacity test
- MN-001 blood concentration sample will be collected at the following timepoints: prior to the first dose and at Hour 0.5, 1.5, 3, 6, 9, 12 and 24 (± 30 minutes) post dose for the first 6 subjects only\*
- Concomitant medication review
- Adverse event review
- Dispense study drug

Once the pre-dose assessments have been completed, the subject will be administered a single dose of MN-001 with room temperature water.

\* The first 6 subjects enrolled in the study will have the option to remain in the clinic overnight until the last PK blood sample is drawn or return the following day for the last/final blood draw.

# Visit 4: Telephone Visit Week 2 ± 3 days

The study nurse/coordinator will telephone the subject to review adverse events and concomitant medications.

# Visit 5: Week 4 ± 5 days

The following assessments will be conducted:

- Body weight /waist circumference
- Vital signs
- Abbreviated physical examination
- 12-lead ECG at hour 1.5 ( $\pm$  30 minutes) post dose
- Fasting safety labs chemistry (including CPK, liver enzymes, lipid panel) hematology, coagulation profile, and urinalysis labs
- Urine pregnancy test (pre-menopausal female)
- Adverse event review
- Concomitant medication review
- Study drug accountability
- Subjects will be instructed to increase their dose to 250 mg bid.

#### Visit 6: Week 8 ± 5 days

- Body weight/waist circumference
- Vital signs
- Abbreviated physical examination
- 12-lead ECG at hour 1.5 ( $\pm$  30 minutes) post dose
- Fasting safety labs chemistry (including CPK, liver enzymes, lipid panel) hematology, coagulation profile, and urinalysis labs
- Urine  $\beta$ -hCG (in pre-menopausal females)
- Adverse event review
- Concomitant medication review
- Study drug accountability

#### Visit 7: Week $12 \pm 5$ days

- Body weight/waist circumference
- Vital signs
- Abbreviated physical examination
- 12-lead ECG at hour  $1.5 \pm 30$  minutes) post dose
- Fasting safety labs chemistry (including CPK, liver enzymes, lipid panel) hematology, coagulation profile, and urinalysis labs
- CK-18 biomarker
- Blood sample for Cholesterol efflux capacity test
- Liver MRI
- Urine  $\beta$  -hCG (in pre-menopausal females)

- Alcohol consumption questionnaire
- Adverse event review
- Concomitant medication review
- Study drug accountability/return of study drug

#### 8.8.1.3. Follow Up Phase

#### Visit 8: Week $13 \pm 3$ days

- Body weight/waist circumference
- Vital signs
- Physical examination
- Adverse event review

#### **Early Termination visit**

Subjects who discontinued study medication will undergo the following assessments:

- Body weight/waist circumference
- Vital signs
- Abbreviated physical examination
- 12-lead ECG
- Fasting safety labs chemistry (including CPK, liver enzymes, lipid panel) hematology, coagulation profile, and urinalysis labs
- CK-18 biomarker
- Blood sample for cholesterol efflux
- Liver MRI
- Urine  $\beta$ -hCG (in pre-menopausal females)
- Alcohol consumption questionnaire
- Adverse event review
- Concomitant medication review
- Study drug accountability /return of study drug

#### Laboratory Re-test visit

Subjects who have an abnormal lab finding will return for a laboratory re-test visit and will have the following assessments performed:

- Fasting chemistry, hematology, or urinalysis lab, as indicated
- Adverse event review

• Concomitant medication review

#### 8.8.2. **Procedures/Assessment Details**

#### 8.8.2.1. Informed Consent

The Principal Investigator or a qualified designee (e.g., a licensed, qualified medical practitioner such as a physician's assistant or a nurse practitioner) listed on Form FDA 1572 will explain the study to the subject, answer all of the subject's questions, and obtain written informed consent before performing any study-related procedure. Informed Consent should be conducted in accordance with local requirements. Subjects should be able to verbally describe the benefits and risks associated with this study and what other treatment alternatives are available (as described in the consent form). Only subjects who provide informed consent, as assessed and documented by the Investigator, will be enrolled.

#### 8.8.2.2. Medical History

A medical history obtained by the PI or qualified designee as listed on the Form FDA 1572.

#### 8.8.2.3. Prior/Concomitant Medication Review

Site study staff will record all medications taken within 1 month prior to screening visit in the CRF. Also, the following parameters will be recorded for all concomitant medications: drug name, route of administration, total daily dose, unit, frequency, start/stop dates, indication, and whether the medication was started after last dose of study medication. The concomitant medications will subsequently be coded using the World Health Organization Drug Dictionary (WHO-DD).

#### 8.8.2.4. Physical Examination

The physical exams must be performed by the PI or qualified designee (physician, physician's assistant or nurse practitioner) listed on the Form FDA 1572. Clinically significant changes from the signing of the informed consent form (ICF) should be captured as AEs in the CRF.

A complete physical examination includes the following assessments: general appearance, head, eyes, ears/nose/throat, neck, lymph nodes, skin, lungs, heart, abdomen, and musculoskeletal. If the subject is discontinued for any reason, every attempt should be made to perform a final physical examination.

#### 8.8.2.5. Vital Signs, Height, and Weight

Blood pressure (BP), heart rate (HR) measurements will be taken in a supine position. Respiratory rate and temperature will also be measured and all measurements will be recorded in the CRF. Clinically significant changes from baseline should be captured as AEs in the CRF.

Weight will be measured in pounds. Height will be recorded only at Visit 1 (screening). Waist circumference will also be recorded.

#### 8.8.2.6. Electrocardiogram (12-Lead ECG)

All subjects will have standard resting 12-lead ECGs performed and interpreted. Subjects are to be supine for at least 5 minutes prior to ECG assessments. The time the ECG is performed will be recorded (using a 24-h clock).

The PI or a qualified designee listed on Form Food and Drug Administration (FDA) 1572 must review, initial, and date the report, which must be filed in the subject's study chart. Clinically significant findings at screening must be captured in the medical history. Any clinically significant changes compared post study drug administration must be captured as an adverse event in the CRF.

#### 8.8.2.7. Fib-4 Index

The Fib-4 index is a non-invasive method for identification of patients with advanced fibrosis. The Fib-4 is a simple formula based on age, AST, ALT and platelets that corresponds with fibrosis stage (Martinez et al 2011).

#### 8.8.2.8. Nonalcoholic fatty liver disease (NAFLD) Fibrosis Score

The NAFLD Fibrosis Score is a validated method of noninvasively estimating the fibrosis stage in a patient with NAFLD. This score calculates a patient's risk of fibrosis based on age, body mass index (BMI), presence of impaired fasting glucose/diabetes, platelets, albumin, ALT and AST (Angulo et al 2007).

## 8.8.2.9. Cytokeratin-18 (CK-18)

Cytokeratin 18 (CK-18) fragment levels correlate with the magnitude of hepatocyte apoptosis and independently predict the presence of NASH.

## 8.8.2.10. Adverse Event (AE) Monitoring

The PI or a qualified designee listed on Form FDA 1572 must assess the severity and relationship to study medication for all AEs (see Section 12.2).

All observed or volunteered AEs regardless of treatment group or suspected causal relationship to the investigational product(s) will be recorded on the AE page(s) of the CRF.

Each PI and research team are responsible for identifying adverse events and reporting them.

For all AEs, the Investigator must pursue and obtain information adequate to determine the outcome of the AE and to assess whether it meets the criteria for classification as an SAE (see Section 12.2) requiring immediate notification to the Sponsor or its designated representative.

For all AEs, sufficient information should be obtained by the Investigator to determine the causality of the AE. The Investigator is required to assess causality and indicate that assessment on the CRF. For AEs with a causal relationship to the investigational product, follow-up by the Investigator is required until the event or its sequelae resolve or stabilize at a level acceptable to the Investigator, and Sponsor concurs with that assessment.

Adverse events (serious and non-serious) including all suspected unexpected serious adverse reactions (SUSARs) should be recorded on the CRF from the date of informed consent until the

end of their participation in the study (i.e., the subject has discontinued or completed the followup visit).

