### Follow-up Visit (Week 13)

All subjects who complete the study will return for a follow-up visit at Week 13. At the last visit a physical examination including body weight, vital signs, and safety labs will be done. Adverse events and concomitant medications will be collected.

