# 6. OVERALL STUDY DESIGN AND PLAN: DESCRIPTION

The study will consist a Screening Phase (up to 4 months) followed by a Treatment Phase (12 weeks), and a Follow-up visit (within 1 week after the last dose).

A total of 40 male and female subjects  $\geq 18$  years of age are planned to be enrolled.

The study phases are described below and displayed in Figure 1 and the Schedule of Assessments is displayed in Table 1.

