# 6.1.3. Follow-up Phase

All subjects who complete the study will return for their final visit at Week 13 for safety assessments and to assess adverse event status and document concomitant medications.

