## 12.3. Recording Adverse Events

Adverse events should be collected and recorded for each subject from the date that the first study dose was taken until the end of their participation in the study (i.e., the subject has discontinued or completed the study). Only those AEs that occurred while on study drug that have not been resolved will be followed until resolution or stabilization.

Following the end of the subject's participation in the study, the PI or an authorized delegate should report SAEs "spontaneously" if considered at least possibly related to study medication.

Adverse events may be volunteered spontaneously by the study subject, or discovered by the study staff during physical examinations or by asking an open, non-leading question such as, "How have you been feeling since you were last asked?" All AEs and any required remedial action will be recorded in the subject's source documentation and transcribed onto the appropriate CRF page for the study period indicated. The nature of AE, date (and time, if known) of AE onset, date (and time, if known) of AE outcome to date, severity, and action taken of the AE will be documented together with the PI or an authorized physician's assessment of the seriousness of the AE and causal relationship to study medication and/or study procedure (at the time of assessment).

All AEs should be recorded individually in the study subject's own words (verbatim) unless, in the opinion of the PI or an authorized physician, the AEs constitute components of a recognized condition, disease, or syndrome. In the latter case, the condition, disease, or syndrome should be named rather than each individual symptom. The AEs will subsequently be coded using the MedDRA.

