## 12.4. Treatment and Follow-Up of AEs

Appropriate measures should be taken to treat AEs as necessary, and the response of the study subject should be monitored and recorded. Clinical, laboratory, and diagnostic measures should be obtained as needed, and the results of which should be recorded in the subject's source documentation and transcribed onto the appropriate CRF page.

All SAEs will be followed until resolution, stabilization of the condition, the event is otherwise explained, or the subject is lost to follow-up.

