## 13.1.4 Safety Analysis

Safety analyses will be conducted on the Safety Analysis Set.

The incidence of treatment-emergent AEs (TEAEs, defined as AEs occurring from the time of first dose through 7 days after the last dose of study medication), SAEs and AEs leading to discontinuations will be summarized by treatment group. Incidence of TEAEs will also be summarized by severity (mild, moderate, or severe), as well as by relationship to treatment (not related, possibly related, or probably related) and by seriousness.

Changes from baseline in laboratory values will be summarized for continuous variables. Lab shift tables showing incidence of new or worsening clinically significant findings from baseline to the last visit will be displayed. Shift from baseline to the highest lab value, and from baseline to the lowest lab value will also be displayed.

Incidence of out-of-normal-range values and markedly abnormal change from baseline in laboratory safety test variables will be tabulated.

Changes in vital signs from baseline to each visit will be summarized by treatment groups.

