### DEFINITIONS

Adverse Event	An adverse event (AE) is any untoward medical occurrence in a subject administered a pharmaceutical product, regardless of causality assessment.		
Full Analysis Set Population	Group of randomized subjects who received at least 14 days of study drug and had at least one post-dose efficacy measurement.		
Safety Analysis Set Population	Group of subjects who received at least one dose of study drug and had at least one post-dose safety assessment.		
PK population	PK sample collection of the first 6 subjects enrolled in the study.		
Serious AE	An AE occurring at any dose that: results in death; is a life-threatening experience; requires inpatient hospitalization or prolongation of an existing hospitalization; results in a persistent or significant disability/incapacity; or is a congenital anomaly/birth defect in the offspring of a patient who received study drug.		
Treatment- emergent AE	AEs occurring from the time of first dose through 7 days after the last dose or that is already present prior to the first dose of study drug and becomes more severe post-dose		

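### Early stoppers have no assured collection of new adverse events through day 7 after the last dose, although TEAEs are defined over that window

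*Combined protocol and SAP*

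**What the plan says.** **Window for counting.** Protocol 13.1.4 (and the synopsis) takes TEAEs to be those "defined as AEs occurring from the time of first dose through 7 days after the last dose of study medication". SAP section 4 uses the same 7 days: "AEs occurring from the time of first dose through 7 days after the last dose or that is already present prior to the first dose", the latter kind counting if it worsens on treatment. Protocol section 11 and SAP 6.2 make TEAEs and TESAEs safety outcomes.

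**End of recording.** Section 8.8.2.10 closes recording at the "end of their participation in the study (i.e., the subject has discontinued or completed the followup visit". Section 12.3 records events "until the end of their participation in the study (i.e., the subject has discontinued or completed the study".

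**Visits after stopping.** Section 6.1.3 says "All subjects who complete the study will return for their final visit at Week 13 for safety assessments", and the synopsis says "All subjects who complete the study will return for a follow-up visit at Week 13". Section 6 and the synopsis methodology describe "a Follow-up visit (within 1 week after the last dose" without limiting it to completers. The ET visit in 8.8.1 applies to subjects who stopped study medication and includes an AE review, safety labs and an ECG. Section 7.3 places it at study discontinuation. No day relative to the last dose is given.

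**Events after participation ends.** Sections 12.3 and 12.5.1 leave later SAEs to spontaneous reporting, and only when judged at least possibly related. Section 12.1, by contrast, calls for AEs in post-treatment follow-up periods to be recorded.

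**The concern.** The counting rule needs 7 days of off-drug event data from every dosed subject. The collection rule, followed literally, does not secure those days in subjects who stop early. A new event that starts after the ET visit but within 7 days of the last dose is a TEAE by definition, yet no scheduled contact would ask about it. If it is serious but judged unrelated, it also falls outside the spontaneous-reporting rule, although TESAEs are counted regardless of causality.

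Subjects removed for intolerance are among those affected. The gastrointestinal criteria in 7.3.1 take a subject out of the study, not only off the drug. An event that is never collected can only lower the count. In a single-arm study of this size, one affected subject missed changes a reported incidence by 1/40 = 2.5 or 1/20 = 5 percentage points.

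**Working it through.** The plan offers no figure to reproduce here. The check compares the rules and then applies simple arithmetic.

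**1. Which rule collects a new event between ET and day 7 in an early stopper?**
- 8.8.2.10 and 12.3: recording has closed at discontinuation.
- 6.1.3 and the synopsis follow-up paragraph: Week 13 is for completers.
- 7.3.3: covers events already present at withdrawal. It refers to section 11 for the procedure, but section 11 contains no follow-up procedure.
- 12.3: continues follow-up only for unresolved events that began on drug.
- Laboratory re-test visit (8.8.1): includes AE review, but needs an abnormal laboratory finding to trigger it.
- 12.3 and 12.5.1: SAEs only, spontaneous, and only if at least possibly related.
- Section 6 and 12.1: point towards collection, but fix neither a day nor a duration, and conflict with the rules above. A visit *within* 1 week can also fall before day 7.

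No rule assures collection through day 7.

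**2. How much of the window does the ET visit cover?** Let t be the days from last dose to ET. Coverage = min(t, 7)/7.

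| t (days) | Coverage |
|---|---|
| 0 | 0/7 = 0% |
| 1 | 1/7 = 14% |
| 3 | 3/7 = 43% |
| 5 | 5/7 = 71% |
| 7 or more | 7/7 = 100% |

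The plan does not set t, so any of these rows is compatible with the text.

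**3. How many subjects?** The plan gives no dropout rate. As an assumption, take all-cause non-completion from protocol Table 3:
- 4-week asthma trial: (147 − 131)/147 = 16/147 = 10.9%
- 8-week interstitial cystitis trial: (305 − 251)/305 = 54/305 = 17.7%

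Expected early stoppers = N × rate, and P(at least one) = 1 − (1 − rate)^N. N is 40 in protocol 13.1.3 and 20 in SAP 8.1.

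| N | Expected | P(at least one) |
|---|---|---|
| 40 | 4.4 to 7.1 | 0.99 to above 0.999 |
| 20 | 2.2 to 3.5 | 0.90 to 0.98 |

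**4. Upper bound on lost time.** If every ET fell on the last-dose day, uncollected time would be 7 days × expected stoppers: about 30 to 50 of 40 × 7 = 280 subject-days, or about 15 to 25 of 20 × 7 = 140. If every ET fell on day 7 or later, it would be zero.

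**5. Completers.** Table 1 allows ±5 days at Week 13 and 8.8.1.3 allows ±3. With Week 12 on time and the last dose taken then, the last AE review can fall 7 − 5 = 2 or 7 − 3 = 4 days later. Completers have a scheduled off-drug contact, but it need not reach day 7.

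**The case against.** A reader might infer that early stoppers get no visit after their last dose, that their off-drug window is empty, and that 2 to 7 subjects would have no off-drug safety data. The documents do not support this. ET is a visit for subjects who stopped study medication, with AE review and safety labs. A subject who stops tablets at home may attend days later. Ongoing on-drug events are followed, and related SAEs remain reportable.

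It is also tempting to say that delayed liver events would be missed. Section 8.6.3 keeps subjects with dosing withheld for liver tests on the scheduled assessments, which include AE review, and adds rechecks at least every 2 weeks. That objection stands for those subjects, with one reservation: section 7.3 lists laboratory abnormalities requiring drug discontinuation among the reasons for withdrawal from the study, so 8.6.3 and 7.3 must be reconciled.

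The earlier trials are a loose guide. Their rates are all-cause, include placebo arms, and come from 500 to 1500 mg/day against 250 to 500 mg/day here. Section 4.2.1 reports that no gastrointestinal event led to discontinuation in the asthma trial. Some non-completers withdraw consent or are lost, and an added contact may not reach them. A biased comparison between completers and stoppers is not shown either: the study has one arm, and completers' own window is not fully assured.

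Finally, 12.4 can be read as the specific rule for SAEs ("All SAEs will be followed until resolution, stabilization of the condition, the event is otherwise explained, or the subject is lost to follow-up"), overriding the general sentence in 12.3. That is reasonable, and makes the 12.3 point one of clarification.

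None of this supplies a rule that collects new events through day 7 in a subject discontinued from the study.

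**Conclusion.** The concern holds in a limited form. The stated collection rule contradicts the stated TEAE window, and the follow-up population is described in two ways. New events through day 7 are therefore not assured in early stoppers, mainly those discontinued from the study under 7.3 and 7.3.1. The data would be incomplete, not absent, with coverage between 0/7 and 7/7 according to an ET day that the plan leaves open.

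The count of about 4 to 7 of 40, or 2 to 4 of 20, rests on borrowed all-cause non-completion rates. It is an illustration of how many subjects could be affected, not an estimate of toxicity stops. The possible effect is an undercount of TEAEs and TESAEs. Its size cannot be derived from the documents. The point should be corrected because it is a conflict between written rules, not merely missing detail, and the remedy is small.

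**What to change.** - **8.8.2.10 and 12.3:** end AE and SAE collection for every dosed subject no earlier than 7 days after the last dose, regardless of discontinuation or causality.
- **Synopsis, 6.1.3 and Table 1:** apply the follow-up contact to all dosed subjects, using the existing Visit 8 assessments. If ET falls before day 7 and the subject declines a visit, use a telephone AE review. Bring these passages into line with section 6 and the synopsis methodology, and settle the Week 13 tolerance between Table 1 and 8.8.1.3 so that the last review reaches day 7.
- **12.3:** state that SAEs starting off drug are followed as in 12.4.
- **7.3 and 8.6.3:** reconcile the two passages, so that it is clear which assessments continue when drug is stopped for laboratory values.

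The cost is a wording amendment and, at the assumed rates, an extra contact for about 2 to 7 subjects. Reported TEAE rates may rise slightly because more of the defined window is observed.
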